**Table 2-2 Acceptable Time Windows for Parameters Other than Data from the Patient Diary**

Time Point	Acceptable Time Window
Pre-dose at Visit 1 (Day 1: Day -2 to Day1)	Predose from Day -2 to Day 1 for safety assessment
Pre-dose at Visit 1 (Day 1)	Predose on Day 1 for efficacy assessment
Post-dose at Visit 1 (Day 1)	QOL assessment with EQ-5D-5L questionnaire: by 0.5 hour post-dose on Day 1 Other measurements: 0.5 to 4 hours post-dose on Day 1
Visit 2 (Day 2)	Day 2
Visit 3 (Day 3)	Between Day 3 and Day 4
Optional-Visit 1 (Day 4)	Day 4
Visit 4 (Day 5)	Between Day 5 and Day 6
Optional Visit 2 (Day 6)	Day 6
Visit 5 (Day 9)	Between Day 7 and Day 11
Visit 6 (Day 15)	Between Day 12 and Day 18
Visit 7 (Day 22)	Between Day 19 and Day 25
Early termination	Date of early termination + 3 days

Measurements collected within the acceptable time window for each scheduled assessment time point, including data obtained at the time of withdrawal, will be used for the analyses of all endpoints at each assessment time point. For all patients with multiple measurements within a visit window, the measurement obtained closest to the target time point will be used. If two measurements collected with the same time deviation exist before and after the target time point, the measurement obtained before the target time point will be adopted for analysis. The assessment time point having no measurements within the corresponding acceptable time window will be considered as missing.

In the patient diary, if there are multiple measurements which may be adopted for a scheduled assessment, even though the above rules have been strictly followed, the measurements of the earlier assessment date or the earlier assessment time of day will be adopted (with the priority given to morning, followed by afternoon, evening, and bedtime, in this order). If multiple measurements collected with the same time (date and hour) for body temperature, the highest measurement will be adopted.

In the assessment of items from other than the patient diary, if there are multiple measurements which may be adopted for a scheduled assessment time point (even though the above rules have been strictly followed), the measurements at the time point entered in the CRF will be adopted.

## 6.4 Handling of Missing Data

Missing data will not be imputed.

- Patients who do not experience alleviation of symptoms will be censored at the last observation time point, except in the case of sensitive analysis for primary analysis.
  - If all symptoms were missing after baseline, time to alleviation of symptoms, time to alleviation of symptoms excluded cough, time to alleviation of the 4 systemic symptoms, time to alleviation of the 3 respiratory symptoms and time to alleviation of individual symptoms will be handled as missing.
- For the sensitive analysis for primary endpoint, the patients who do not experience alleviation of symptoms will be treated as follows.
  - If patients who discontinue from the study and still have influenza symptoms, time to alleviation of symptoms will be censored as 14 days.
  - In consideration of treatment duration of the oseltamivir group.
    - If patients who discontinue until Day 5 and still have influenza, time to alleviation of symptoms will be censored at the last observation time point.
    - If patients who discontinue after Day 5 and still have influenza, time to alleviation of symptoms will be censored as 14 days.
  - In consideration of the reason of the discontinuation.
    - If patients discontinue due to AE or lack of efficacy, time to alleviation of symptoms will be censored as 14 days.
    - If patients discontinue due to other reason, time to alleviation of symptoms of the patients will be censored at the last observation time point.

### 6.4.1 Handling of Virology Test Data in Consideration of the Stability Window

Sample processing time is defined as the time between the time of sample collecting and the time of sample aliquotting recorded in the shipment manifest from Eurofins. Any quantitative virus titer and quantitative PCR samples processed within 96 hour as sample processing time will be included for analysis. The qualitative PCR before initial dosing is excluded from the 96 hour turn-around requirement. All qualitative PCRs before initial dosing will be considered evaluable regardless of sampling and aliquotting time.

- If the time of sample aliquotting is not recorded at Eurofins, sample processing time will be treated as missing.

## **6.5 Definition**

### **6.5.1 Display of Days of Study**

The date of the first dose and the day before the first dose of the S-033188/Placebo will be designated as Day 1 and Day -1, respectively.

### **6.5.2 Baseline**

For influenza symptoms scores, the measurement entered in the CRF is defined as baseline. If there are influenza symptoms scores entered in the e-Diary prior to the initial dosing, these measurements will not be used for analysis.

For body temperature, assessment of health and EQ-5D-5L, the measurement with the following two conditions is defined as baseline. If there are multiple measurements which may be adopted, the measurement obtained at the earliest time will be used, otherwise measurements prior to the initial dosing will not be used for analysis.

- Data observed when e-diary is set up
- Data observed when first administration and sending are occurred on the same day

For assessment of health prior to influenza symptoms, the measurement with the following condition is defined as health status prior to influenza symptoms. If there are multiple measurements which may be adopted, the measurement obtained at the earliest time will be used.

- Data observed when first administration and sending are occurred on the same day

For efficacy assessments other than above, baseline is defined as the measurement obtained before the first administration at Visit 1 (predose).

For safety assessments other than above, baseline is defined as the last measurement obtained before the first administration.

## **7. DEMOGRAPHIC VARIABLES AND OTHER BASELINE CHARACTERISTICS**

### **7.1 Subject Disposition**

- 1) Among all randomized subjects, the numbers of subjects who complete the study and subjects who discontinue the study will be tabulated by treatment group. For subjects who discontinue the study, reasons for withdrawal will also be tabulated by treatment group.
- 2) The number and percentage of subjects included in each of the ITTI and the PPS Populations among all randomized subjects will be calculated for the S-033188 group and Placebo group. For the subjects excluded from each population, the

reason for exclusion will be summarized. Fisher's exact test will be performed with a two-sided significance level of 0.15 to check differences among the treatment groups regarding the distribution of subjects in the ITTI and the PPS Populations. For the patients aged 20 to 64 years, the similar analyses will be applied in the S-033188 group and Oseltamivir group.

- 3) The number and percentage of subjects included in the Safety population among all randomized subjects will be calculated by prescribed treatment group. For the subjects excluded from the Safety population, the reason for exclusion will be summarized. For patients who receive at least one dose of the study drug, the treatment that the patients actually received will be defined as prescribed treatment. For patients who don't receive one dose of the study drug, the treatment to which the patients were randomized will be defined as prescribed treatment.

## 7.2 Demographic and Baseline Characteristics

The following demographic and baseline characteristics among the ITTI and Safety Populations will be summarized using descriptive statistics for the S-033188 group, Oseltamivir group and placebo group. For quantitative data, the descriptive statistics will be calculated. For qualitative data, the frequency of each category and the percentage of subjects in each category among all subjects included in the analysis population will be presented.

For the patients aged 20 to 64 years in the ITTI Population, the following demographic and baseline characteristics will be summarized in the same manner.

- Continuous variable  
Age, height, body weight, BMI, total score of influenza symptoms and body temperature
- Categorical variable  
Age, body weight, sex, region, race, ethnicity, time to treatment from flu onset, presence or absence of flu vaccination, prior drug, prior therapy, medical history, smoking habits, presence or absence of meal before initial study treatment, duration between meal and administration (hours) (definition: absolute value of "time of dosing on Day 1" minus "time of meal obtained closest to the time of dosing on Day 1"), composite symptom scores, presence or absence of meal after initial study treatment, influenza virus subtype based on RT-PCR and influenza virus subtype based on RIDT (Rapid Influenza Diagnostic Test).

## 8. STUDY CONDUCT

### 8.1 Treatment Exposure and Compliance

The duration of treatment exposure will be summarized with descriptive statistics by the S-033188 group and oseltamivir group for the safety population.

The duration of treatment exposure [day] is defined as the dosing period during which a subject took medication as follows;

$$\{(final\ dose\ date) - (initial\ dose\ date) + 1\}$$

If a patient does not take any study drug, the duration of treatment exposure will be defined as 0.

The treatment compliance rate will be summarized with descriptive statistics by the treatment group for the safety population. In addition, the frequency of each category and the percentage of subjects in each category among all subjects included in the analysis population will be presented.

The treatment compliance rate [%] is defined as;

$$100 \times \{(\text{actual frequency of treatment exposure}) / (\text{expected frequency of treatment exposure by early discontinuation of treatment})\}$$

## 8.2 Medical History

Prior and concomitant medical histories will be coded using the MedDRA Version 19.1. Medical history (concurrent and previous disease) will be presented by treatment group for the Safety population.

## 8.3 Prior and Concomitant Medication

Prior and concomitant drugs will be coded using the World Health Organization (WHO) Drug Dictionary. Medication consists of drug and therapy. Prior medication is defined as all medications taken before Day 1 of study administration. Concomitant medication is defined as all medications taken on Day 1 or later. The drug and therapy can be also classified as both prior and concomitant.

For Safety population, the number of subjects who took prior drug and concomitant drug, and corresponding proportion will be summarized by WHO class and preferred term for each treatment group. For Safety population, the number of subjects who took prior therapy and concomitant therapy, and corresponding proportion will be summarized for each treatment group.

For ITTI Population, frequency of acetaminophen use will be summarized for each treatment group. Even though the date or time of acetaminophen use is missing, the frequency is counted. Wilcoxon rank sum test will be used to compare in frequency between the S-033188 group and the placebo or the Oseltamivir group. The two-sided significance level will be set at 0.15 in these analyses.

## 9. EFFICACY ANALYSIS

In the ITTI Population that is the primary analysis population, the primary endpoint and all secondary endpoints will be analyzed. For the PPS that is a secondary analysis population, only the primary endpoint will be analyzed. Table 3 summarizes the primary

endpoint, secondary endpoints, other endpoints and statistical methods used to analyze these endpoints. The detailed statistical methods are described in later sections.

The analysis of each efficacy endpoint will consist of comparison between the S-033188 group (40 mg and 80 mg combined) and the placebo group using data of the two age strata pooled (i.e., 12 to 64 years age), and comparison between the S-033188 group (40 mg and 80 mg combined) and the oseltamivir group using data of 20 to 64 years age stratum.

**Table 3 Statistical Methods Used to Analyze Each Endpoint**

	Endpoint Analysis	Statistical Method
Primary Endpoint	Time to alleviation of symptoms	1, 2, 9, 10, 11
Secondary Endpoints	Proportion of patients positive for influenza virus titer	3, 13
	Proportion of patients positive by RT-PCR	3, 13
	Change from baseline in virus titer	4, 12
	Change from baseline in the amount of virus RNA (RT-PCR)	4, 12
	Area under the curve adjusted by baseline in virus titer	4, 12
	Area under the curve adjusted by baseline in the amount of virus RNA (RT-PCR)	4, 12
	Time to cessation of viral shedding by virus titer	1, 9, 10,11
	Time to cessation of viral shedding by RT-PCR	1, 9, 10,11
	Proportion of patients whose symptoms has been alleviated	3, 13
	Time to alleviation of the 4 systemic symptoms	1, 9, 10,11*
	Time to alleviation of the 3 respiratory symptoms	1, 9, 10,11*
	Change from baseline in composite symptom score	6, 12
	Time to resolution of fever	1, 9, 10,11
	Proportion of patients reporting normal temperature	3, 13
	Body temperature	6, 12
Time to alleviation of individual symptoms	1, 9, 10,11*	
Time to return to preinfluenza health status	1, 9, 10,11*	
Incidence of influenza-related complications	5, 13	
Other Endpoints	Serum influenza antibody titer	7, 13, 14
	Polymorphic and treatment-emergent amino acid substitutions in the PA gene of evaluable virus	13
	Drug susceptibility in patients with evaluable virus	12
	EQ-5D-5L and EQ VAS	12
	Work productivity questionnaire	12
	Intrahousehold infection rate	8

\* Treatment group difference in median time

[Statistical test methods]

1. Stratified Peto-Prentice's generalized Wilcoxon test

2. Stratified log rank test
3. Mantel-Haenszel test
4. van Elteren test
5. Fisher's exact test
6. Analysis of covariance (ANCOVA)
7. Wilcoxon rank sum test
8. Poisson regression model  
    [Summarization methods]
9. Kaplan-Meier curve
10. Median time and its 95% CI
11. Treatment group difference in median time and its 95% CI (Bootstrap method)
12. Summary statistics (continuous variables)
13. Summary statistics (categorical variables)
14. Geometric mean

## 9.1 Primary Endpoint

The primary efficacy endpoint is the time to alleviation of symptoms (unit: hours), which is defined as the time between the initiation of the study treatment and the alleviation of influenza symptoms. The alleviation of symptoms is defined as the time when all of 7 influenza symptoms (cough, sore throat, headache, nasal congestion, feverishness or chills, muscle or joint pain, and fatigue) have been assessed by the patient as 0 (None) or 1 (Mild) in the patient eDiary, for a duration of at least 21.5 hours (24 hours – 10%).

### 9.1.1 Analyses of Primary Endpoint

#### 9.1.1.1 Primary Analysis

Time to alleviation of symptoms will be compared between the S-033188 group and the placebo group using the stratified Peto-Prentice's generalized Wilcoxon test with composite symptoms score at baseline ( $\leq 11$  or  $\geq 12$ ) and region (Japan/Asia or Rest of the world) as stratification factors. Patients who do not experience alleviation of symptoms will be censored at the last observation time point. If at least one of the 7 influenza symptom scores is missing at date and time of assessment that patients have, missing assessments of influenza symptoms conservatively will be treated as having moderate or severe symptoms (as failures) at the corresponding date and time of assessment.

[Comparison between the S-033188 group and the placebo group]

```
proc lifetest data = analysisdata;
  where TRTP in ("S-033188", "Placebo");
  time TIME * CENSOR (0);
  strata SCOREC REGION / group = TRTP test = PETO ;
run;quit;
```

- TRTP: Treatment group
- TIME: Time to alleviation of symptoms

- SCOREC: Category of baseline composite symptom score ( $\leq 11$  or  $\geq 12$ )
- REGION: Category of region (Japan/Asia or Rest of the world)

The same analysis in PPS will be performed as a sensitivity analysis.

#### **9.1.1.2 Secondary Analysis**

Time to alleviation of symptoms will be compared between the S-033188 group and the Oseltamivir group using the stratified Peto-Prentice's generalized Wilcoxon test with composite symptoms score at baseline ( $\leq 11$  or  $\geq 12$ ) and region (Japan/Asia or Rest of the world) as stratification factors. Patients who do not experience alleviation of symptoms will be censored at the last observation time point. If at least one of the 7 influenza symptom scores is missing at date and time of assessment that patients have, missing assessments of influenza symptoms conservatively will be treated as having moderate or severe symptoms (as failures) at the corresponding date and time of assessment.

The same analysis in PPS will be performed as a sensitivity analysis.

#### **9.1.1.3 Other Analysis**

The Kaplan-Meier survival curve will be plotted for each treatment group, and the median time to alleviation of symptoms and its 95% CI will be calculated. The Greenwood method will be used in the calculation of the CIs. In addition, the treatment group difference in median time and its 95% CI will be estimated. The 95% CI of difference of median time will be obtained by the bootstrap percentile method. The 10,000 bootstrap samples will be generated by the following SAS code. A random seed of 16010831 and 16010832 will be used for comparison between the S-033188 and the Placebo or the Oseltamivir, respectively. Then, the treatment group difference in median time will be calculated by each bootstrapped sample and its 95% CI will be constructed using percentiles of the bootstrap distribution.

```
proc surveysselect data = analysisdata seed = 16010831 out = bootstap method = urs  
  rate = 1.0 rep = 10000 outhits;  
  strata TRTP;  
run;quit;
```

- TRTP: Treatment group

The same analysis in PPS will be performed as a sensitivity analysis.

#### **9.1.1.4 Sensitivity Analysis**

- 1) Time to alleviation of symptoms will be compared between the S-033188 group and the placebo group using the stratified log rank test with composite symptoms score at baseline ( $\leq 11$  or  $\geq 12$ ) and region (Japan/Asia or Rest of the world) as stratification factors. Patients who do not experience alleviation of symptoms will

- be censored at the last observation time point. The same analysis will be applied to compare the S-033188 group with the Oseltamivir group.
- 2) If patients who discontinue from the study and still have influenza symptoms, they will be treated as follows in the similar analysis at section 9.1.1.1, 9.1.1.2 and 9.1.1.3 (excluding analyses of PPS population and 95% CI for group difference in median time).
- If patients who discontinue from the study and still have influenza symptoms, time to alleviation of symptoms will be censored as 14 days.
  - In consideration of treatment duration of the Oseltamivir group.
    - If patients who discontinue until Day 5 and still have influenza, time to alleviation of symptoms will be censored at the last observation time point.
    - If patients who discontinue after Day 5 and still have influenza, time to alleviation of symptoms will be censored as 14 days.
  - In consideration of the reason of the discontinuation.
    - If patients discontinue due to AE or lack of efficacy, time to alleviation of symptoms will be censored as 14 days.
    - If patients discontinue due to other reason, time to alleviation of symptoms of the patients will be censored at the last observation time point.
- 3) Time to alleviation of symptoms excluding cough will be compared between the S-033188 group and the placebo group using the stratified Peto-Prentice's generalized Wilcoxon test with composite symptoms score at baseline ( $\leq 11$  or  $\geq 12$ ) and region (Japan/Asia or Rest of the world) as stratification factors. Patients who do not experience alleviation of symptoms will be censored at the last observation time point. If at least one of the 6 influenza symptom scores is missing at date and time of assessment that patients have, missing assessments of influenza symptoms conservatively will be treated as having moderate or severe symptoms (as failures) at the corresponding date and time of assessment. The same analysis will be applied to compare the S-033188 group with the Oseltamivir group. This alleviation of symptoms excluding cough is defined as the time when all of 6 influenza symptoms (sore throat, headache, nasal congestion, feverishness or chills, muscle or joint pain, and fatigue) have been assessed by the patient as 0 (None) or 1 (Mild) in the patient eDiary, for a duration of at least 21.5 hours (24 hours – 10%).

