7.8 Withdrawal of Patients from the Study or Study Drug

The investigator will make every reasonable attempt to complete the study for each enrolled patient. A patient may withdraw for any reason. The investigator will advise the sponsor about the withdrawal of any patient by the IRT.

The investigator will withdraw a patient from the study or the study drug treatment for any of the following reasons:

- A serious or intolerable AE occurs and the investigator considers that the patient should be withdrawn because of the AE.
- The patient requests to be withdrawn from the study.
- The patient becomes lost to follow-up.
- The investigator determines that the patient should be withdrawn based on the management and discontinuation criteria for abnormal liver function tests (Appendix 5).
- The investigator determines that the patient should be withdrawn because of other reasons.

In the event of a patient's withdrawal, the investigator will promptly notify the sponsor and will make every effort to complete the early termination assessments. All patients withdrawn due to AEs will be followed until resolution of the AEs, until the unresolved AEs are judged by the investigator to have stabilized, or the patient becomes lost to follow-up. The date of completion (for patients who completed the study), date of discontinuation (for patients who discontinued from the study prematurely), period of discontinuation, and reason for discontinuation will be entered in the eCRF. Completion of the study for each patient is defined as the case that the patient completed the follow-up period.

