7.8.1 Clinical Progression or Lack of Response

In cases where on clinical review, patients appear to be deteriorating clinically or have not responded to the study drug, the investigator should consider the possibility of

secondary infections, decompensation of underlying conditions, or progression of influenza. Patients should be assessed, and investigations should be performed as clinically indicated.

In the event an investigator considers that the influenza has not responded and wishes to treat with open-label oseltamivir (not provided by the sponsor), the patient should stop all blinded study drugs. Since unblinding of the study drugs would not alter the management of the patients, unblinding in this situation is discouraged, and the patients should remain in the study for follow-up as described in Section 7.8. Such cases should be discussed urgently with the sponsor or sponsor's designated Medical Monitors.

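### The lack-of-efficacy sensitivity scenario misses non-responders who start open-label oseltamivir and stay in the study

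*SAP*

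**What the plan says.** SAP 9.1.1.4 2) opens with its trigger: "If patients who discontinue from the study and still have influenza symptoms, they will be treated as follows". Three scenarios follow. The first censors all such patients at 14 days. The second depends on whether they left by Day 5 or later. The third depends on the reason: "If patients discontinue due to AE or lack of efficacy, time to alleviation of symptoms will be censored as 14 days", with last-observation censoring for other reasons. SAP 6.4 lists the same rules under missing data, also keyed to leaving the study ("If patients who discontinue from the study and still have influenza symptoms, time to alleviation of symptoms will be censored as 14 days"), and introduces them as rules for patients without alleviation.

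In the primary analysis the only censoring rule is: "Patients who do not experience alleviation of symptoms will be censored at the last observation time point". Nothing there, or in the oseltamivir comparison, deals with antiviral rescue.

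Protocol 7.8.1 covers the non-responder. If the investigator "wishes to treat with open-label oseltamivir (not provided by the sponsor), the patient should stop all blinded study drugs". It adds that "the patients should remain in the study for follow-up as described in Section 7.8". Protocol 7.8 treats leaving the study and stopping drug as different things ("The investigator will withdraw a patient from the study or the study drug treatment for any of the following reasons") and also says "A patient may withdraw for any reason".

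Protocol 6.2.1 prohibits systemic antivirals from Day 1 to Day 22. SAP 5.1 removes patients who took prohibited medication from the per-protocol set.

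**The concern.** A scenario labelled lack of efficacy should deal with the route for non-response that the protocol itself describes. Here the two documents do not meet. The SAP rule starts when a patient leaves the study, and Protocol 7.8.1 tells sites to keep the rescued non-responder in it. That patient's alleviation under a second antiviral is then credited to the arm to which he or she was randomised.

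Counting outcomes after rescue is a legitimate choice for the primary analysis. The problem is that no sensitivity analysis shows what happens if those outcomes are instead scored as failures. The S-033188 v oseltamivir comparison is the more exposed of the two. It is the second step of the hierarchy for submissions outside Japan, and its planned power is only 42.1% to 87.2% (Protocol Table 9-1).

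**Working it through.** **1. Trace one patient through every analysis.** Take a patient who does not respond, starts open-label oseltamivir, stays in the study and later meets the alleviation definition.

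| Analysis | Treatment of this patient |
|---|---|
| Primary and secondary, ITTI (SAP 9.1.1.1, 9.1.1.2) | Event at the time of alleviation after rescue; only patients without alleviation are censored |
| Sensitivity 1), log-rank | Same |
| Sensitivity 2), all three scenarios | Outside the trigger (did not leave), so same |
| Sensitivity 3), excluding cough | No rescue rule, so an event at the six-symptom alleviation time |
| Per-protocol set | Excluded for prohibited medication, not scored as a failure |

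A rescued patient who never alleviates is censored at the last diary entry, which is close to 14 days if the diary is complete. The gap therefore concerns rescue followed by alleviation.

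**2. Does another reading of discontinue close the gap?** The third scenario does not itself repeat that the study is meant. If it meant stopping drug, two obstacles remain. SAP 6.4 limits the rules to patients without alleviation. Also, patients aged 12 to 19 take a single Day 1 dose, and adults finish on Day 5 or 6, so later rescue leaves no blinded drug to stop.

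**3. Reproduce the plan's own figures.** Inputs from Protocol 9.2: exponential times, medians 72 and 100 h, 2:1 allocation (412:206), follow-up 336 h, two-sided 0.05. For a Peto-Prentice weighted test with pooled survival S = aS1 + (1−a)S0 and p = aS1/S:

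power = Φ( √N · |∫ S·aS1·(1−p)·(λ1−λ0) dt| / √(∫ S²·p(1−p)·[aS1λ1 + (1−a)S0λ0] dt) − 1.96 )

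The smallest N with power of at least 0.90 is 618 (power 0.9003; simulated 0.898), as stated. With 350 per arm the formula gives 0.421, 0.548, 0.674, 0.785 and 0.872, which matches all five rows of Table 9-1.

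**4. Illustrate the size.** None of the following assumptions comes from the documents. A share q of patients unalleviated at 72 h starts open-label treatment, and their remaining time is divided by 1.2: t′ = 72 + (t − 72)/1.2. Rule A is the SAP as written. Rule B censors rescued patients at 336 h. Both rules are applied to the same 1,500 simulated trials per row, without strata.

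Expected number rescued, for example against oseltamivir at 68 v 84 h with q = 10% v 5%: 350 × 2^(−72/68) × 0.10 + 350 × 2^(−72/84) × 0.05 = 16.8 + 9.7 = 26.5 of 700 (simulated mean 26.7).

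| Comparison | q, S-033188 / control | Power A → B | Median difference A → B (h) |
|---|---|---|---|
| Placebo | 2% / 2% | 0.905 → 0.900 | 28.7 → 29.3 |
| Placebo | 5% / 5% | 0.913 → 0.909 | 28.0 → 30.0 |
| Placebo | 5% / 10% | 0.907 → 0.942 | 27.9 → 32.0 |
| Placebo | 10% / 10% | 0.907 → 0.879 | 28.2 → 31.8 |
| Placebo | 10% / 20% | 0.886 → 0.941 | 27.5 → 36.3 |
| Oseltamivir | 5% / 5% | 0.680 → 0.658 | 15.7 → 16.4 |
| Oseltamivir | 10% / 5% | 0.685 → 0.532 | 15.9 → 16.5 |
| Oseltamivir | 10% / 10% | 0.675 → 0.627 | 15.5 → 16.9 |
| Oseltamivir | 5% / 10% | 0.654 → 0.737 | 15.6 → 17.0 |

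Monte Carlo error on one power is √(0.68 × 0.32 / 1500) ≈ 0.012 in the oseltamivir rows. The median difference rises in every row because the assumed switch at 72 h falls at or after the S-033188 median, so rule B moves mainly the control median. The power column is the better guide.

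**The case against.** The strongest reply is that these scenarios handle missing data. SAP 6.4 places them there, and Protocol 9.4 promises a sensitivity rule for missing data and nothing more. A rescued patient who keeps filling in the diary has no missing outcome, and analysing the observed outcome is a recognised choice. This stands as a defence of the primary analysis, and it makes the point a request to widen one scenario, not the correction of an error. It does not supply the missing check: a scenario that singles out lack of efficacy is already making a statement about treatment failure.

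The second reply is that rescue is partly handled. The per-protocol analysis covers both comparisons, and SAP 8.3 tabulates concomitant drugs by arm. This also stands, within limits. Exclusion after randomisation is not the same as scoring a failure, and the tabulation does not show whether rescue came before alleviation.

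Third, a reader might infer that the scenario never reaches treatment failures, or that it must reproduce the primary result whatever the failure rate. The documents do not support this. A patient may withdraw for any reason, and Protocol 7.8.1 says only that rescued patients should stay. Those who leave unalleviated for an adverse event or lack of efficacy do move to 14-day censoring.

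Fourth, a reader might infer that the gap flatters S-033188 against placebo. If placebo patients are rescued more often, it does the opposite: the written rule gives the lower power (0.907 v 0.942 at 5% / 10%).

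**Conclusion.** The gap is real but partial. The third scenario misses non-responders who start open-label oseltamivir and stay in follow-up. Their later alleviation counts as an ordinary event in every ITTI analysis. Patients who leave the study for an adverse event or lack of efficacy are covered.

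The size cannot be known from the documents, which give no rescue rate. Under the assumptions above, re-keying leaves power against placebo between 0.879 and 0.942. Against oseltamivir it shifts power by 0.532 − 0.685 = −0.153 or 0.737 − 0.654 = +0.083 when rescue differs between arms, so the direction is open. If rescue turns out to be rare, the added analysis will change little, and that is worth showing. The primary test is not put in doubt. Label: cheap improvement.

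**What to change.** In SAP 9.1.1.4 2), third scenario, and in the matching text of 6.4, for both comparisons:

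- Also treat as lack of efficacy, censored at 14 days, any patient who starts non-study anti-influenza treatment before alleviation, even if the patient stays in the study and later alleviates.
- Do not require that blinded drug was stopped. That condition would miss patients aged 12 to 19 and adults who have finished dosing.
- State whether discontinue means the study or the study drug.
- Report the number of such patients by arm in the ITTI population.
- Leave the primary analysis unchanged.

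Separately, the prohibition of systemic antivirals in Protocol 6.2.1 and the open-label provision in 7.8.1 should be reconciled.

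The cost is a short SAP amendment before unblinding and one derived flag. Protocol 6.2 already collects drug name, duration and reason for use. If the clock time of the first dose is not recorded, the SAP needs a rule for a start on the same date as alleviation. The downside is a sensitivity result that may be less favourable to S-033188.
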